ABT-263 induces apoptosis, rather than lysis of circulating platelets, which differs from typical chemotherapy induced thrombocytopenia related to myelosuppression. Limited human clinical data are available to understand the response to infusion of exogenous platelets in the presence of circulating drug levels. Platelet transfusion studies conducted in beagle dogs demonstrated that transfusion of one-day old platelets administered near the time of ABT-263 C_{max} , resulted in higher platelet levels than dogs not receiving supplemental platelets. Platelet concentrations remained higher after 24 hours with declining ABT-263 concentrations. This study suggests that infusion of platelets may have beneficial effects in treating acute thrombocytopenia following oral dosing with ABT-263.

From the pre-clinical models, there may be an opportunity in the monotherapy setting to increase efficacy without additional platelet toxicity in the setting of continuous dosing. In murine xenograft models of SCLC, 21 days of continuous dosing achieves superior tumor growth inhibition, greater increase in life span, and greater incidence of complete and overall response rates compared to the intermittent dosing schedules or 14 days of dosing and 7 days off drug. In a dog toxicology study, ABT-263 was delivered once daily for 28 days. At doses that achieve plasma concentrations within the targeted efficacious exposure range, circulating platelet counts recovered to baseline within 14 days of dosing and remained at baseline for the subsequent 14 days of dosing.

This observation of platelet recovery during continued ABT-263 dosing has also been observed in the Phase 1 clinical studies. Given that platelet nadirs typically occur in the first few days of dosing and circulating platelet counts recover during continued dosing, a lead-in period may help reduce the depth of platelet nadir.

ABT-263 Toxicology

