Adjustments to the dose escalation schedule may also be made based upon preliminary pharmacokinetic and safety data obtained from concurrent dose escalation studies that are being conducted with ABT-263. These decisions will be based on the judgment of the AbbVie Medical Monitor in consultation with the investigator.

Subject assessments for safety and clinical progression will continue weekly through the first 2 cycles (6 weeks). Subsequently, subject assessments for safety and clinical progression will be performed once every cycle (every 3 weeks) or more frequently, as needed.

Phase 1 -14/21 Day Dosing

ABT-263 will be administered for 14 consecutive days followed by 7 days off drug to complete a 21-day cycle. Subjects will be instructed to self-administer ABT-263 orally once daily (QD) within 30 minutes after the completion of breakfast.

Figure 3. ABT-263 Dosing Schematic – Phase 1

Additionally, a continuous dosing regimen will be evaluated and compared to the 14/21 cyclic dosing regimen.

Phase 1 – 21/21 Day Continuous Dosing

Once either the MTD is defined or dosing in the 4th dose level is completed for the 14/21 day dosing schedule, whichever occurs first, a continuous dosing schedule will be assessed. Dosing with ABT-263 under the continuous dosing schedule (21/21 day) will begin at the dose estimated to provide exposure equivalent to the highest dosing level cleared (4th dose level) or the MTD from the 14/21 day schedule. For example, if the highest dose level cleared or the MTD from the 14/21 day dosing schedule is 375 mg, the continuous starting dose (defined Cycle 1 Day 1 dose) would be $(375 \times 14)/21$ or 250 mg. A minimum of three subjects will be enrolled in each cohort. The ABT-263 dose will be

escalated using a modified CRM as described previously for the 14/21 day regimen (Figure 2).

Prior to beginning the assigned 21/21 day continuous dosing regimen, a 7-day lead-in dose titration period will be implemented. In preclinical experiments in which stepwise increases in ABT-263 doses were administered to dogs every one or two weeks, the thrombocytopenic effect of higher doses was significantly attenuated. These data combined with the clinically observed rebound in platelet counts from nadir during continued ABT-263 dosing suggest that a lead-in period may help reduce the depth of the initial platelet nadir and provide an additional margin of safety.

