Subjects will begin dosing at 100 mg on Lead-in Day 1 (LD1). This is the dose level at which a mean maximal platelet drop of approximately 60% from baseline with recovery during 14 days of dosing is expected based on observations in this study to date. The lead-in titration dose may be adjusted if the defined dose level fails to significantly mitigate ABT-263-induced thrombocytopenia following the lead-in period or the defined dose level results in significant occurrence of DLT in the lead-in period.

A subject may only proceed from the lead-in period to the defined dose level for Cycle 1 Day 1 and beyond if platelet count is $\geq 50,000/\text{mm}^3$ after Lead-in Day 7 and stable or increasing. If the platelet count is $< 50,000/\text{mm}^3$ after Lead-in Day 7, the visit day will be considered Lead-in Day 8 and the subject will continue to receive the lead-in dose until the platelet count is $\geq 50,000/\text{mm}^3$.

When the platelet count is $\geq 50,000/\text{mm}^3$, the subject will receive the lead-in dose that day, and the next day (defined as Cycle 1 Day 1) the subject will receive the defined dose for Cycle 1 Day 1, provided the pre-dose platelet count that day is $\geq 50,000/\text{mm}^3$ and platelets are stable or increasing. For example, if a subject's platelet count is $\geq 50,000/\text{mm}^3$ on Lead-in Day 9, the subject will take the lead-in dose on Day 9. The next day will be considered Cycle 1 Day 1 and the subject will begin receiving the defined dose for Cycle 1 Day 1. However, if the pre-dose platelet count is $< 50,000/\text{mm}^3$ or

[figure not shown]
platelets are decreasing, then the day becomes Lead-in Day 10 and the subject continues dosing at the lead-in dose.

If the platelet count is $< 50,000/\text{mm}^3$ after 14 days at the lead in dose, the lead in dose will become the subject's dose for the duration of the study. To change from the lead in dose to a higher dose (for subjects who continue receiving the lead in dose beyond the lead in period), a discussion between the investigator and the AbbVie Medical Monitor is required.

The period for defining DLTs will be the total days dosed in the lead-in period plus 21 days dosed in Cycle 1 (28 days if subject moves to Cycle 1 Day 1 after the planned 7 day lead-in period).

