- Study procedures (except platelets) may be performed within 72 hours prior to Day 1 for each cycle. Platelets counts must be performed within 24 hours prior to dosing on Day 1 of each cycle.
- Height will be assessed at Screening only.
- A symptom directed physical exam may be performed weekly through Cycle 2.
- ECG will be performed at Screening, Lead-in Day 1, Day 1 and Day 14 of Cycle 1, Day 1 and Day 14 of Cycle 3 and at the Final Visit. Every effort should be made to obtain all ECGs approximately 4-8 hours post-dose (however, 6-8 hours post-dose is preferred), and if possible at approximately the same time of day. If pharmacokinetic data indicates the C_{max} of parent drug or a major metabolite occurs at a time different than this specified range, the timing of the ECG may be modified. Repeat ECGs will be performed whenever clinically necessary.
- 2D Echocardiogram with Doppler will be performed at Screening, Lead-in Day 1, Day 1 and Day 14 of Cycle 1, Day 1 and Day 14 of Cycle 3 and at the Final Visit. Every effort should be made to obtain all echocardiograms approximately 4-8 hours post-dose (however, 6-8 hours post-dose is preferred), and if possible at approximately the same time of day. If pharmacokinetic data indicates the C_{max} of parent drug or a major metabolite occurs at a time different than this specified range, the timing of the echocardiogram may be modified. Repeat echocardiograms will be performed whenever clinically necessary.

Table 2. Schedule of Assessments – 21/21 Day Dosing with Lead-in Period (Phase 1) (Continued)

- g. Platelet counts will be performed at Screening, Lead-in Days 1, 2, 3, 5 and 7 and then daily if the lead-in period extends beyond Day 7. Cycle 1: Pre-dose on Days 1, 2, 3, 5, 8, 14 (in addition, at all PK time points per [Table 4](#)), Day 16, and as needed. Subsequent Cycles: Weekly and as needed. If the investigator and the AbbVie Medical Monitor jointly agree that platelet counts through Cycle 4 have been stable, then the frequency of platelet counts in Cycle 5 and beyond may be decreased to Day 1 of each cycle and as needed. If platelet count on any given day is less than 50,000/mm³, additional platelet counts should be performed every day or at the discretion of the investigator.
- h. Lymphocyte enumeration will be performed at Screening, Day 14 of Cycle 1, end of Cycle 4, the end of every 3rd cycle thereafter and at the Final Visit.

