A 7 day period of dosing with a lead-in dose of ABT-263 will be explored with the 21/21 day dosing schedule in order to interrogate whether higher doses may then be given with overall less reduction in platelet counts. Subjects will begin dosing at 100 mg on Lead-in Day 1 (LD1). This is the dose level at which a mean maximal platelet drop of approximately 60% from baseline with recovery during 14 days of continued dosing is expected based on observations in this study to date. The lead-in titration dose may be adjusted if the defined dose level fails to significantly mitigate ABT-263-induced thrombocytopenia following the lead-in period or the defined dose level results in significant occurrence of DLT in the lead-in period.

Phase 2a

Once the MTD and/or RPTD is declared on the Phase 1-21/21 day continuous dosing schedule, a safety analysis will be performed as described in Section 8.1.4. The results of the safety analysis as well as the recommended Phase 2 dose and dosing schedule will be communicated to all participating research sites prior to the start of enrollment in the Phase 2a portion of the study.

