8.1.4 Safety

Safety summaries will include all subjects participating in the study unless otherwise indicated. A safety analysis will be performed for all subjects in the Phase 1 portion of the study once the MTD is reached and/or RPTD is determined, after the last enrolled subject completes one cycle of drug, and prior to enrollment of subjects into the Phase 2a portion of the study. A second safety analysis will be performed for all subjects in the

Phase 1 and Phase 2a portions of the study upon completion of the study. The following will be included in these analyses:

Adverse Events

The number and percentage of subjects having treatment-emergent adverse events will be tabulated by MedDRA system organ class and preferred term.³⁸ The tabulations will also be provided with further breakdowns by NCI CTCAE toxicity grade and relationship to study drug. Serious adverse events, events leading to discontinuation of treatment, and events leading to death, will be summarized. For subjects who participate in Cycle 1 of Phase 1 of the study, all summaries will be done by dose. For the study as a whole, summaries will be provided with a breakdown as appropriate.

Platelet Counts

Platelet counts will be explored for trends with dose and time and summarized as appropriate. The baseline value (last measurement before the beginning of study drug administration) will be included in the statistical analysis and changes from baseline will be addressed.

A repeated measures model with dose level as a classification variable will be performed for values in Cycle 1 of the platelet counts for which multiple measurements will be taken. A transformation of a variable will be used if it clearly provides more nearly symmetric probability distribution and/or more nearly homogenous variances across dose levels.

The relationship between drug concentration variables and platelet counts will be explored. The dependence of observations from the same subject will be appropriately taken into account in all of the above analyses.

Other Safety Measurements

Laboratory test results, lymphocyte enumeration results, vital signs, echocardiogram results, and ECG interval measurements results will be explored for trends with dose and

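### The platelet repeated-measures model covers Cycle 1 only and has no schedule term, so it cannot measure the overall platelet reduction across lead-in plus Cycle 1 or separate the two schedules at 200 mg and 250 mg

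*Protocol*

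**What the plan says.** Section 8.1.4 of the protocol (Platelet Counts) specifies one platelet model: "A repeated measures model with dose level as a classification variable will be performed for values in Cycle 1 of the platelet counts". It names no term for schedule or lead-in. The baseline is the last value before any study drug. Section 5.3.1.1 makes this the pre-dose value on Cycle 1 Day 1 for 14/21 and on Lead-in Day 1 for 21/21. The SAP text does not describe this model.

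The lead-in comes before Cycle 1. Section 5.1 says: "Prior to beginning the assigned 21/21 day continuous dosing regimen, a 7-day lead-in dose titration period will be implemented". Its purpose in Section 5.6.4 is "in order to interrogate whether higher doses may then be given with overall less reduction in platelet counts". Section 3.0 gives the reason: "Given that platelet nadirs typically occur in the first few days of dosing", with recovery as dosing continues. Sections 5.1 and 5.6.4 put the expected mean maximal fall at the 100 mg lead-in dose at about 60%.

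The step up depends on platelets. Section 5.1 begins the rule with "A subject may only proceed from the lead-in period to the defined dose level for Cycle 1 Day 1 and beyond" and requires a count of at least 50,000/mm³ that is stable or rising. Subjects still below 50,000/mm³ after 14 days stay on the lead-in dose.

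**The concern.** Schedule determination is a Phase 1 objective (Section 4.0), and Section 5.1 says that continuous dosing will be compared with 14/21. A model confined to Cycle 1 looks at different stages of exposure in the two schedules. For 14/21 it starts at the first dose. For 21/21 it starts after at least a week on drug, and the values at the cohort dose come only from subjects whose platelets met the step-up rule. Part of any apparent platelet advantage of 21/21 would then come from where the window starts.

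Also, 200 mg and 250 mg were used on both schedules (Section 3.0). A model classified by dose level alone pools subjects with and without a lead-in at those two levels, which are the only ones that allow a same-dose comparison. Section 8.1.4 does not say which dose level applies to subjects who never left the lead-in dose.

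**Working it through.** **Window.** Section 5.1 sets the DLT period for 21/21: "The period for defining DLTs will be the total days dosed in the lead-in period plus 21 days dosed in Cycle 1", given as "28 days if subject moves to Cycle 1 Day 1 after the planned 7 day lead-in period". The check is 7 + 21 = 28 days, which reproduces the protocol's figure. It confirms that the lead-in is separate from Cycle 1. The platelet model therefore omits the first 7 of 28 days on drug (25%).

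**Sampling days, Phase 1 21/21.** Table 2, footnote g, says: "Platelet counts will be performed at Screening, Lead-in Days 1, 2, 3, 5 and 7". Lead-in Day 1 pre-dose is the baseline, which leaves 4 lead-in days (2, 3, 5, 7). Cycle 1 has 7 days (1, 2, 3, 5, 8, 14, 16).
- Share outside the model: 4 / (4 + 7) = 4/11 = 36%.
- If the lead-in runs to Day 14 with daily counts: (4 + 7) / (11 + 7) = 11/18 = 61%.

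**Scheduled counts, same cohorts.** The same footnote adds counts at the PK times in Table 4 (0, 2, 4, 6 and 8 h on Cycle 1 Days 1 and 14).
- Cycle 1 counts: 5 + 1 + 1 + 1 + 1 + 5 + 1 = 15.
- Share outside the model: 4 / (4 + 15) = 4/19 = 21%.

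**Contrast with 14/21.** Cycle 1 sampling covers Days 2 to 6 after the first dose, all inside the model.

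**Shared doses (Section 3.0).** 14/21: 10, 110, 200, 250 mg. 21/21: 125, 200, 250, 300 mg. Two levels overlap.

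**Illustration of the effect on a worst-fall comparison.** Let F be the worst percent fall without a lead-in and C the worst fall in Cycle 1 after one, at the same dose. Both are assumed; only the 60% lead-in fall is the protocol's. As a simplification, mean falls are treated as if they were one subject's.
- Apparent benefit, Cycle 1 only: F − C.
- Apparent benefit, whole window: F − max(60, C).
- F = 75, C = 50: 75 − 50 = 25 points against 75 − 60 = 15 points.
- F from 70 to 80 and C from 40 to 70: 0 to 40 points against 0 to 20 points.
- The two agree whenever C is 60 or more, so the distortion could be nil.

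**The case against.** Much of the case on the other side stands.

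- **Mitigation after the lead-in.** A reader might infer that the model cannot show mitigation at all. The documents do not support that. Sections 5.1 and 5.6.4 judge mitigation after the lead-in, which is Cycle 1, and the baseline is pre-drug, so the fall at the cohort dose is inside the model. What is missed is the overall fall. The absence of a schedule term still weakens the comparison after the lead-in.
- **Decisions.** A reader might infer that the recommended Phase 2 dose or schedule was biased. No passage ties a decision to this model. Sections 5.1, 5.6.1 and 6.7.5 rest the recommended dose on DLTs and/or the MTD, confirmed Grade 4 thrombocytopenia is a DLT (Section 6.7.1), and the 21/21 DLT period includes the lead-in.
- **Individual counts.** A reader might apply the 60% fall to each subject, for example 75,000 × 0.4 = 30,000 at the entry limit. The figure is a mean and does not predict individual counts.
- **Other analyses.** Lead-in values are not lost. Section 8.1.4 explores platelets by dose and time without a Cycle 1 limit. The SAP takes maximum grades from the first dose and tabulates adverse events by schedule. But the exploration is unspecified, the grade shifts span all treatment, and the SAP summarises laboratory data by dose and study portion, not by schedule. None of these answers the question of overall reduction.
- **Reason for the Cycle 1 limit.** The factor is dose level, and the cohort dose starts on Cycle 1 Day 1. Simply extending the window would credit 100 mg counts to cohorts at 125 to 300 mg. This is right, and the fix has to deal with it.
- **Selection.** Subjects who miss the platelet threshold stay on study at the lead-in dose. The selection applies to counts at the cohort dose, not to study membership, and the number affected is not given.

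**Conclusion.** The point holds in a limited form. As written, the model cannot measure overall platelet reduction over lead-in plus Cycle 1, and it does not separate the schedules at 200 mg and 250 mg. The omission is 36% of scheduled sampling days, or 21% of scheduled counts, for Phase 1 21/21 with the planned 7-day lead-in. Unscheduled counts are ignored in both figures. How far this flatters 21/21 depends on falls that the documents do not give, and it may be zero.

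The consequence is confined to the descriptive comparison of schedules. Even a well-specified model would be weak evidence. The cohorts are sequential and non-randomised with a minimum of 3 subjects, and the SAP reports 29 Phase 1 subjects, which over the eight dose-by-schedule groups listed in Section 3.0 is 29/8, or about 3.6 per group. This is an inexpensive improvement to make; it does not undermine the dose finding.

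**What to change.** In Section 8.1.4, and in the SAP if the model is run:

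1. Add schedule (14/21 against 21/21 with lead-in) as a factor alongside dose level. Keep the Cycle 1 model for the cohort-dose effect.
2. Add an analysis from the first dose to the end of Cycle 1, on days since first dose, with the dose actually being taken as a time-varying term. Lead-in counts at 100 mg are then not attributed to the cohort dose.
3. Report the lowest count and the largest percent fall from the pre-first-dose baseline by schedule, with 200 mg and 250 mg side by side. Give both over the whole window and over a common number of days since first dose, because a 28-day window gives more chance of a low value than a 21-day one.
4. For this summary, keep subjects who stayed on the lead-in dose in their assigned cohort, and state when their window ends.
5. Label the comparison descriptive, because the cohorts are small, sequential and non-randomised.

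The cost is a wording change and a modest amount of extra analysis on counts already collected. Dosing and visits do not change. The 21/21 platelet profile may look less favourable than under the Cycle 1 model alone.

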The safety of ABT-263 has been evaluated in single- and repeat-dose (up to 6 and 9 months in duration in rats and dogs, respectively), reproductive (male and female fertility and embryo fetal development), safety pharmacology (cardiovascular, neurofunctional, and pulmonary), genetic (Ames, in vitro cytogenetics, and in vivo micronucleus), and special studies (guinea pig sensitization; lymphocyte immunophenotyping; and single-dose oral toxicity in male rats). The primary effects of ABT-263 were on the hematopoietic system (platelets and lymphocytes) and the male reproductive system (germ cell depletion), and are believed to be based on inhibition of one or more members of the Bcl-2 family of antiapoptotic proteins. Other findings included ovarian atrophy (rats only), and generally minimal and reversible liver changes (single-cell hepatocellular necrosis, increased mitotic index, and hypertrophy/hyperplasia and pigmentation of Kupffer cells) and single-cell necrosis in various tissues. ABT-263 was neither genotoxic, nor did it affect male or female fertility in rats or embryo-fetal development in rats and rabbits. ABT-263-related effects were observed on brain, testes, and circulating platelets in juvenile rats. Effects on the brain (cerebellar hypoplasia), which were not observed in adult rats, were the likely result of incomplete maturation of the blood-brain-barrier at the time dosing was initiated in the rat pups (post natal Day 7).

ABT-263 caused increases in pulmonary and peripheral vascular resistance and decreases in cardiac output in the dog following acute or multiple daily dosing. Despite the increases in vascular resistance, there were no increases in blood pressure. On Day 28 of the oral dosing study, these cardiovascular effects were associated with a mean C_{\max} value of 16.6 $\mu\text{g/mL}$, whereas no statistically significant hemodynamic changes were associated with a mean C_{\max} of 11.4 $\mu\text{g/mL}$.¹³ Similar systemic exposures induced these effects in the acute cardiovascular study.

Chronic Lymphocytic Leukemia (CLL)

Chronic lymphocytic leukemia (CLL) is a monoclonal disorder characterized by a progressive accumulation of functionally incompetent lymphocytes. It is the most

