16.1__9 Documentation of Statistical Methods

16.1__9.1 Statistical Analysis Plan

All statistical tests were two-tailed and were performed at significance level of 0.05, unless otherwise indicated. Computation for the statistical tests was performed with the SAS, Version 9.20 or above on a Hewlett Packard workstation using the Unix operating system. For the analysis of variance (ANOVA), SAS procedure GLM with type III sums of squares was utilized. SAS procedure PROC UNIVARIATE and PROC MEANS were used to obtain summary statistics. SAS procedure PROC FREQ was used for analysis of categorical variables. SAS procedure PROC LIFETEST was used for survival analysis.

Data Sets Analyzed

Subjects who took at least one dose of navitoclax were included in the efficacy, safety, and pharmacokinetics summaries.

All 29 subjects enrolled and treated in the Phase 1 portion of the study were analyzed for safety, efficacy, and pharmacokinetics. All 31 subjects enrolled and treated in the Phase 2 portion of the study were analyzed for safety, and efficacy while 25 subjects who had at least one PK result for any visit were included in PK analysis.

Demographic Variables

All baseline summary statistics are based on characteristic prior to the first dose of navitoclax. Descriptive statistics were provided for baseline characteristics and demographic variables for the Phase 1 and the Phase 2 portions of the study separately. Age, height, and weight (female, male, and together), Beta-2 microglobulin, baseline lymphocytes were summarized with means, medians, standard errors, standard deviations, and ranges. Frequencies and percentages were provided for gender and race, ethnicity, age ranges, nicotine and alcohol use, bulky lymphadenopathy (nodes >5 cm), CD38, IGVH, ZAP70, staging - Binet, staging - RAI, and protocol version.

Medical History

Following analysis was provided for each portion of the study. Medical history data was summarized and presented using primary MedDRA system organ classes (SOCs) and preferred terms (PTs). The number and percentage of subjects experiencing events were summarized by dose and overall.

Previous Treatment and Concomitant Medications

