- Subject deaths occurring ≤ 30 days after last dose of study drug.
- Subject deaths occurring > 30 days after last dose of study drug.
- Any treatment-emergent DLT adverse events by primary MedDRA system organ class and preferred term.

Selected Adverse Events

Analysis of adverse events of safety areas of interest were conducted through the summary of MedDRA preferred terms identified using standard MedDRA queries (SMQs) and custom searches. Like TEAEs analyses, overview of selected AEs, and selected AEs by primary MedDRA system organ class and preferred term were provided. The search criteria for each of the safety areas of interest were described below.

Identified Risks

Thrombocytopenia - PTs: 10043554 Thrombocytopenia; 10035528 Platelet count decreased

Neutropenia - PTs: 10001507 Agranulocytosis; 10016288 Febrile neutropenia; 10029354 Neutropenia; 10059482 Neutropenic infection; 10049151 Neutropenic sepsis; 10029366 Neutrophil count decreased

Lymphopenia - PTs: 10025327 Lymphopenia; 10025256 Lymphocyte count decreased

Potential Risks

Hemorrhagic Events - SMQ 20000038 Hemorrhages (Narrow)

Opportunistic Infections - SMQ 20000235 Opportunistic Infections (Broad)

Tumor Lysis Syndrome - SMQ 20000219 Tumor Lysis Syndrome (Narrow)

Hepatotoxicity - SMQ 20000006 Drug Related Hepatic Disorders – Comprehensive (Broad); SMQ 20000007 Drug Related Hepatic Disorders – Severe Events Only (Narrow)

Increased Pancreatic Enzymes - SMQ 20000022 Acute Pancreatitis (Narrow)

Cardiovascular Events - SMQs: 20000004 Cardiac Failure (Narrow); 20000130 Pulmonary Hypertension (Narrow)

Venous Thromboembolic Events - SMQ 20000084 Embolic and Thrombotic Events, Venous (Narrow)

Cerebellar Hypoplasia - PT 10008033 Cerebellar Hypoplasia

Decreased Spermatogenesis - SMQ 20000210 Fertility Disorders (Narrow; males only)

Skin Cancer or Second Malignancies - SMQs: 20000173 Skin Neoplasms, Malignant and Unspecified (Broad); 20000090 Malignancies (Broad)

Allergic Reactions - SMQ 20000021 Anaphylactic Reaction (Broad)

Drug Interactions - HLT 10022528 Interactions

Analysis of Laboratory and Vital Signs Data

The value for baseline used in laboratory and vital sign analyses is defined in the Definition of Baseline section. All laboratory and vital signs were summarized by dose and the study portion as a whole.

Analysis of Mean Changes from Baseline in Clinical Laboratory Data

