Changes from baseline were analyzed for each scheduled post-baseline visit and for the final visit for lymphocyte enumeration, urinalysis, blood chemistry and hematology parameters, as well as vital sign parameters.

Laboratory tests to be summarized are included in Table 1.

Table 1. Clinical Laboratory Tests

Hematology	Chemistry	Urinalysis
Hematocrit	Blood Urea Nitrogen (BUN)	Urine PH
Hemoglobin	Creatinine	Urine specific gravity
Red Blood Cell (RBC) count	Total bilirubin	Lymphocyte Enumeration
White Blood Cell (WBC) count	Serum glutamic-pyruvic transaminase (SGPT/ALT)	B-Lymphocytes total
Neutrophils	Serum glutamic-oxaloacetic transaminase (SGOT/AST)	Natural killer cells total
Bands	Alkaline phosphatase	T-Helper cells total
Lymphocytes	Sodium	T-Lymphocytes total
Monocytes	Potassium	T-Suppressor cells total
Basophils	Calcium	
Eosinophils	Inorganic phosphate	
Platelet count	Uric acid	
Reticulocyte count	Cholesterol	
Prothrombin time (PT)	Total protein	
Activated partial thromboplastin time (aPTT)	Glucose	
Mean corpuscular volume (MCV)	Triglycerides	
MPV	Albumin	
MCH	Lactate dehydrogenase (LDH)	
MCHC	Magnesium	
	Chloride	
	Bicarbonate	
	Lipase	

Mean changes from baseline at each scheduled post-baseline visit and Final Visit was summarized with the baseline mean, visit mean, change from baseline mean, standard deviation, and minimum/maximum values.

Analyses of Shift from Baseline in Clinical Laboratory Data

For shifts relative to National Cancer Institute Common Toxicity Criteria for Adverse Events (NCI CTCAE), baseline and post-baseline laboratory observations were categorized as grade 0, grade 1, grade 2, grade 3, or grade 4 according to NCI CTCAE grade version 3.0.

The baseline and final grades were defined respectively as the grade of the last measurement collected prior to the first dose of navitoclax, and as the last post-baseline

measurement collected no more than 30 days after the last dose of navitoclax. The maximum NCI toxicity grade value was the value with highest NCI toxicity grade collected after the first dose of navitoclax and within 30 days following the last dose of navitoclax. In cases where multiple values are collected on the same day, the maximum grade value was selected as the value for that day.

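### The SAP omits, without explanation, the protocol's Cycle 1 platelet model, the concentration-platelet exploration, any ECG or echocardiogram summary, and amylase

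*Protocol*

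**What the plan says.** Protocol 8.1.4 has a platelet part and a part on other safety measurements.

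- **Platelet model.** "A repeated measures model with dose level as a classification variable will be performed for values in Cycle 1 of the platelet counts". The baseline value is to enter the analysis, and a transformation is allowed if it clearly improves symmetry or homogeneity of variance.
- **Exposure.** "The relationship between drug concentration variables and platelet counts will be explored".
- **Correlation.** "The dependence of observations from the same subject will be appropriately taken into account in all of the above analyses".
- **Cardiac measurements.** "echocardiogram results, and ECG interval measurements results will be explored for trends with dose and" time, and summarised as appropriate, with changes from baseline addressed.

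Protocol Table 7 lists both amylase and lipase.

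The SAP's change-from-baseline analysis covers "lymphocyte enumeration, urinalysis, blood chemistry and hematology parameters, as well as vital sign parameters". It consists of descriptive statistics at each visit, presented by dose and for the study portion as a whole, followed by CTCAE shift tables and grade 3 to 4 listings. The only regression or analysis-of-variance model it describes has pharmacokinetic parameters as the response. It never mentions ECG or echocardiogram. Its Table 1 lists lipase but not amylase, although its list of potential risks includes increased pancreatic enzymes.

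**The concern.** Thrombocytopenia is the toxicity the protocol expects to be dose-limiting. The 7-day lead-in was added to see whether higher doses can then be given with less platelet loss (Protocol 5.6.4). How counts move with dose, time and exposure is therefore a central safety question, and the schedule is dense enough to address it. Means at separate visits do not estimate a dose effect across the series, do not use the correlation between counts from one subject, and do not relate counts to concentration.

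On the cardiac side, the Introduction reports that "ABT-263 caused increases in pulmonary and peripheral vascular resistance and decreases in cardiac output in the dog". The protocol schedules ECGs and echocardiograms in both phases and plans to summarise them, but under the SAP as written no group summary of either would be produced.

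**Working it through.** No sample size, power or error rate is at issue. The check is an item-by-item comparison and a count of the scheduled measurements affected.

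| Item | Protocol | SAP |
|---|---|---|
| Cycle 1 platelet model, dose level as class variable | Will be performed (8.1.4) | Not described |
| Concentration against platelets | Will be explored (8.1.4) | Not described |
| Within-subject dependence in the platelet analyses | To be accounted for (8.1.4) | Not described |
| ECG intervals, echocardiogram | Explored by dose and time, summarised as appropriate (8.1.4) | Neither is mentioned |
| Amylase | Table 7 | Absent from Table 1 |
| Platelet changes from baseline | To be addressed (8.1.4) | Kept, by visit and dose |
| CTCAE grade shifts | Planned (8.1.4) | Kept |

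The SAP names the SAS procedures GLM, UNIVARIATE, MEANS, FREQ and LIFETEST. GLM can fit some repeated-measures models, so this list alone proves nothing. The point is that no such analysis of platelets is described.

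**Laboratory lists.** Chemistry has 22 tests in protocol Table 7 and 21 in SAP Table 1, and the one missing is amylase. Haematology has 18 in each, with no difference.

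**Scheduled Cycle 1 platelet counts per subject** (Protocol 5.3.1.1 and Table 4). In Phase 1, counts at 2, 4, 6 and 8 hours on Days 1 and 14 add 4 + 4 = 8.

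- Phase 1, 14/21: Days 1, 2, 3, 4, 5, 6, 8, 14, 16 = 9 days; 9 + 8 = 17 counts.
- Phase 1, 21/21: Days 1, 2, 3, 5, 8, 14, 16 = 7 days; 7 + 8 = 15 counts. Lead-in Days 1, 2, 3, 5 and 7 give 5 more, outside the planned Cycle 1 model.
- Phase 2a: Days 1, 2, 3, 5, 8, 15 = 6 counts, with 5 more in the lead-in.

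**Platelet counts paired with concentration, Phase 1 Cycle 1.** Five times on Day 1 and five on Day 14 give 10. The Day 2 pre-dose sample makes 11 if the platelet count is drawn alongside it.

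**ECG and echocardiogram visits per subject who stays on study.**

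- Phase 1, 14/21, after the first two cohorts: Screening, C1D1, C1D14, C3D1, C3D14, Final = 6.
- Phase 1, 21/21: the same plus Lead-in Day 1 = 7.
- Phase 2a: Screening, C1D15, C5D1, C9D1, Final = 5.

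**Amylase.** Screening, C1D14 or C1D15, Final = 3 visits.

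**Data per dose level.** The SAP reports 29 Phase 1 subjects. The Introduction lists four completed levels on each schedule, eight in all, so 29 / 8 is about 3.6 subjects per level.

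**The case against.** The strongest reply is that the SAP keeps most of what matters. Platelets are summarised by visit and by dose, with shifts to final and to maximum grade, grade 3 to 4 listings, a DLT table and a thrombocytopenia search. Cardiac failure and pulmonary hypertension are searched, which fits the dog finding, and so is acute pancreatitis. ECGs and echocardiograms are reviewed as they arrive by the medical monitor and an independent cardiology expert. MTD selection uses the DLT-based CRM and no platelet model. With about 3.6 subjects per level, a rich model would be imprecise. Apart from the platelet model, the protocol promises only exploration.

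All of this stands as a limit on the point, but it does not answer it. Protocol 6.1.1 counts laboratory abnormalities as adverse events only under stated conditions, so adverse-event searches do not replace summaries of the measurements. Ongoing individual review yields no group result. Small numbers argue for a simple model, or for a stated reason not to fit one.

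A reader might also infer more than the documents support:

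- That platelet analysis was dropped, or replaced by visit means. Change from baseline and grade shifts were themselves planned, and they were kept.
- That the missing items all concern predicted toxicities measured at many visits. The Introduction's list of potential side effects from preclinical evidence names neither cardiac nor pancreatic effects. The dog effect was seen at a mean peak concentration of 16.6 µg/mL, against about 6.5 expected in humans (16.6 / 6.5, about 2.6 times). Amylase has only 3 visits.
- That the protocol promised lead-in data or a dose-by-time interaction in the model. It specifies Cycle 1 values and dose level as a class variable.
- That lipase goes unanalysed because SAP Table 2 gives no limit for it. Lipase is in Table 1, and shifts are graded by CTCAE.
- That every measurement is already in the database. CRF capture of QT and QTc is stated only for Phase 2a. For echocardiograms, only a judgment of clinical significance is stated.

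**Conclusion.** The point holds as a gap between protocol and SAP. Four planned items are missing without a reason: the Cycle 1 platelet model, the concentration-platelet exploration, any summary of ECG intervals or echocardiogram results, and amylase. The first matters most, because it is stated as an analysis that will be performed and concerns the expected dose-limiting toxicity. The concentration-platelet and cardiac items were promised as exploration, and amylase is minor.

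The loss is 15 or 17 scheduled Cycle 1 counts per Phase 1 subject without the planned model, at least 10 concentration-platelet pairs per subject unused, and 5 to 7 cardiac visits per subject with no group summary. These are scheduled numbers; they assume the subject stays on study and the visits took place.

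Dose selection is not put in doubt. The SAP is written in the past tense, so the finding is that it does not describe these analyses. The documents do not show whether any were run and reported elsewhere.

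**What to change.** Add to the SAP:

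1. The 8.1.4 repeated-measures model of Cycle 1 platelet counts, with dose level as a class variable, baseline included, within-subject correlation allowed for and a transformation if needed. Keep it simple, given 29 Phase 1 subjects over eight dose-schedule levels.
2. A concentration-platelet analysis on the samples paired at pharmacokinetic times, again allowing for repeated observations.
3. Change-from-baseline summaries of the ECG intervals held in the database (QT and QTc at least for Phase 2a), and by-visit summaries of the echocardiogram findings recorded on the CRF.
4. Amylase in Table 1.

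List any item not run as a change from the protocol, with its reason.

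The cost is programming time on data already captured. Echocardiogram measurements, or Phase 1 ECG intervals, that are not on the CRF would have to be extracted from reports. This fix does not require that.
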